Systematic Assessment for Treatment and Emergent Events (SAFTEE): The SAFTEE as modified for Project COMBINE (Johnson et al., 2005) will be performed weekly, **and twice-monthly during study months 4-6** to identify any adverse symptoms. If participants report experiencing adverse symptoms since the previous visit, the research nurse will record the symptom as well as the date of onset, severity, and resolution (if applicable) and research psychiatrist will review it at least weekly and more frequently if symptoms are present.

Timeline Follow--Back (TLFB): The Timeline Followback method (Litten and Allen, 1992) will gather self-- reported opioid use data for each day during the month prior to study enrollment and each day during the study period. The TLFB confirmed by urine toxicology will be the primary outcome measure of psychoactive substance use and will be performed at **every study visit**.

Therapist Contact Log (TCL): The number and duration of treatment sessions will be documented by the therapist on a contact log.

End of Study Form (ESF): At study completion or the point of termination for patients who relapse or drop out, the research psychiatrist fills out an End of Study Form, which indicates whether or not a patient completed 25 weeks of treatment, the date of termination, the number of weeks of treatment completed from randomization to termination, and reasons for early termination, including documented relapse to opiates, resumption of buprenorphine maintenance, psychiatric worsening, medical worsening, or lost to follow--up.

Self--Report

Clinical Global Impression--Self (CGI--S): The CGI--Self is a two--item scale that asks the subject to rate his or her current level of symptoms and estimate changes from baseline (Guy, 1976). The CGI--S will serve as the primary self--reported measure of overall functioning.

Medical Outcomes Study--Sleep Scale (MOS--SS): The MOS--SM is a 12--item measure for characterizing the quality of sleep (Hays et al., 2005). Opioid withdrawal, both acute and protracted is characterized by insomnia and other sleep disturbances. The MOS--SM will be the primary outcome of sleep quality and length and will be collected at each visit.

Craving Scales-- Self: A visual analog scales is used for patients to rate the intensity of craving for opiates experienced since the previous visit ([name] et al., 2011).

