study visits vitals and a urine toxicology for opioids (morphine, oxycodone, buprenorphine, methadone, propoxyphene, and fentanyl), THC, cocaine, benzodiazepines, amphetamines, and metamphetamines will be collected. They will have scheduled meetings with a study psychiatrist weekly to inquire about medication effects and any changes in their medical/psychological condition following medication discontinuation.

The primary outcome will be the percent of patients successfully transitioned off buprenorphine and abstinent from any opioids at the 25-week trial endpoint. Secondary outcomes will include measures of opioid withdrawal, mood, anxiety and sleep problems, abstinence from other substances, time to relapse or dropout, and adverse effects. We hypothesize that more patients will successfully discontinue buprenorphine in the group that received XR-NTX.

This proposed exploratory trial will be able to inform the design of future research and clinical work. A positive signal that transition from maintenance buprenorphine to XR-NTX is feasible and prevents relapse would encourage a larger trial to replicate and perhaps extend to multiple community based treatment settings. A feasible, well-tolerated, and effective method of helping patients wishing to discontinue treatment with BUP has the potential to expand the population of opioid-dependent individuals benefitting from treatment.

A2. Primary and Secondary Outcome Measures

Primary Outcome: percent of patients successfully transitioned off buprenorphine and abstinent from any opioids at the 25-week trial endpoint.

Secondary Outcomes: 1) Measures of weekly opiate withdrawal (SOWS), mood (Ham-D, BDI), anxiety (HAM-A, STAI), and sleep (MOS-SS) (continuous, longitudinal); 2) Time to relapse (survival outcome); 3) Continuing abstinence at 12 and 25 weeks (dichotomous); 4) Dichotomous weekly summary measure of use (derived by combining urine and self-report, as measured by TLFB) reflecting whether each patient had urine-confirmed opiate-free weeks over the course of treatment and urine-confirmed abstinence from all drugs (dichotomous, longitudinal); 5) Adverse events (SAFTEE) (dichotomous).

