The primary purpose of this proposed R21 is to estimate the 95% confidence interval (CI) for the treatment effect size, in this case the odds ratios of treatment success. The resulting 95% CIs provide considerably more information than hypothesis tests; it provides a range of plausible parameter estimates. Such range of effect sizes (especially the estimates from the lower end of the 95% CIs) can be used to conservatively estimate potential effect size in larger clinical trials. The following power calculations are only in support of this study proposal and for the purpose of sample size calculation. We assume that the observed proportion of successful BUP discontinuation in the buprenorphine taper group ranges from 30-50% (we assume higher success rate than in the previous buprenorphine taper studies due to longer period of stabilization). With 25 subjects in each arm, we have 80% power to detect a significant treatment success difference of 37% (e.g. 40% of treatment success in BUP compared to 77% treatment success in XR-NTX arm) on 5% level of significance. This is a robust effect that would be clinically meaningful.

The primary aim of this pilot study is to evaluate feasibility, tolerability, acceptability, and safety of two methods of discontinuing treatment with buprenorphine. The proposed sample size of 60 enrolled and 50 individuals randomized to two treatment arms can provide useful information for subsequent confirmatory clinical trial. We have chosen this sample size to minimize the cost and also to reach the study end within two years. 50 randomized subjects will provide large enough sample size to estimate the potential effect size in 95% confidence interval with reasonable precision.

B. TRIAL MANAGEMENT

B1. Data Collection Centers

All data will be collected at one site: New York State Psychiatric Institute's Outpatient Substance Abuse Research Service (STARS)-downtown at [name]. In our center, we have adopted StudyTrax, a comprehensive electronic system for clinical trials, which we will use to collect and manage data. As many entry forms and study calendars are already programmed, starting of a study can be expedited. Data will be analyzed using SPSS-PC, SAS, and HLM.

B2. Projected Time Table

Based on the recent rate of recruitment in our center and the planned sample size the study is estimated to take 24 months to complete.

B3. Target Population Distribution

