Study Aim #2: To determine whether treatment with XR-NTX reduces severity of protracted withdrawal seen following BUP discontinuation.

Significance testing and preliminary analysis:

All tests for main effects will be performed at two-tailed significance $\alpha=5\%$. We will examine all variables for outliers, the distributions of all continuous variables will be checked for normality and if needed transformations will be used before applying parametric techniques. The distribution of demographic variables and other covariate measures at baseline in the treatment arms will be examined (means, standard deviations, proportions and 95% confidence intervals). The analysis will be adjusted by three preselected covariates (primary opioid type, length of BUP maintenance, and average dose).

Primary Analyses

Subjects treated with XR-NTX will have significantly higher rates of successful transition off BUP at the end of study compared to subjects tapered off BUP. The effect of treatment on the primary outcome will be examined using logistic regression adjusted for specified covariates (primary opioid type, length of BUP maintenance, and average dose), and described using the estimated coefficients of the treatment term in the model, the corresponding odds ratios, and 95% confidence intervals.

Secondary Analyses

Longitudinal dichotomous and continuous outcomes will be modeled with generalized linear mixed effects models using appropriate link function (logit for dichotomous outcomes) with treatment, time, treatment by time interaction, and applicable baseline outcome measure as predictors. Time to relapse will be analyzed using survival analyses and Kaplan-Meier estimators. Dichotomous outcomes will be analyzed similarly to primary hypothesis with logistic regressions. The within subject correlation will be modeled using autoregressive AR(1) structure and random effects of subject. Significant time by treatment interaction indicates different change over time between treatment groups. If the interaction between time and treatment is not found to be significant, the interaction term will be omitted and an overall treatment effect will be tested.

D. QUALITY ASSURANCE

D1. Procedures in place to ensure the validity and integrity of the data

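### Adverse events are to be compared between arms only as a yes/no outcome by logistic regression, so if the arms are observed for different lengths of time the odds ratio mixes event risk with retention.

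*SAP*

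**What the plan says.** - SAP A2, Secondary Outcomes, item 5 reads "Adverse events (SAFTEE) (dichotomous". Item 4, the weekly drug-use measure, is labelled longitudinal as well; item 5 is not. Adverse events are therefore one yes/no per patient and fall outside the mixed models.
- SAP C3, Secondary Analyses: "Dichotomous outcomes will be analyzed similarly to primary hypothesis with logistic regressions". The primary model is described as "using logistic regression adjusted for specified covariates (primary opioid type, length of BUP maintenance, and average dose". It has treatment and three baseline covariates, with no offset, censoring or weeks observed.
- SAP C3 names a time-to-event method for one outcome only: "Time to relapse will be analyzed using survival analyses and Kaplan-Meier estimators".
- The data for a time-based analysis exist. For SAFTEE, the Protocol (Assessment Instruments) says that "the research nurse will record the symptom as well as the date of onset, severity, and resolution (if applicable". The End of Study Form records the termination date and "the number of weeks of treatment completed from randomization to termination".
- Participation can end before week 25. The End of Study Form is completed at termination for patients who relapse or drop out (Protocol, Assessment Instruments). Removal follows about three weeks' absence or hazardous continued drug use (Protocol, Criteria for Early Discontinuation; SAP F3, Study Discontinuation). It also follows a positive naloxone challenge after a missed injection (Protocol, Risks; SAP F1).

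**The concern.** A patient seen for 6 weeks without an event counts the same as one seen for 25 weeks without an event. If one arm is observed for less time, fewer of its patients will have an event recorded even when the weekly risk is identical, and the logistic model assigns that difference to treatment. A reader of the odds ratio could not tell toxicity from retention.

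This matters because SAP A4 gives safety and tolerability, with feasibility and acceptability, as the pilot's primary aim and wants its estimates to inform a confirmatory trial. The two regimens also differ in when patients are most likely to leave: a one-week induction in one arm and a five-week taper in the other.

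**Working it through.** **The plan's own figure.** SAP A4 gives 80% power with 25 per arm for "40% of treatment success in BUP compared to 77% treatment success in XR-NTX arm". Unpooled normal approximation: SE = √[(0.40×0.60 + 0.77×0.23)/25] = 0.129; 0.37/0.129 − 1.96 ≈ 0.90; power 81.7%. The exact power of the uncorrected chi-square is 80.5%. The figure reproduces. It concerns the primary outcome; the SAP gives no power or precision figure for adverse events.

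**Inputs.** From the documents: 25 per arm, 25 weeks, success s = 0.40 (taper) and 0.77 (XR-NTX). Assumed, because the documents give no values: the 25-week event risk R (equal in both arms), when events occur, who leaves and when. Primary failure is used as a stand-in for leaving.

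**Case 1: constant hazard, all failures leave evenly over weeks 0 to 25.** Mean follow-up is 0.40×25 + 0.60×12.5 = 17.5 weeks (taper) and 0.77×25 + 0.23×12.5 = 22.1 weeks (XR-NTX). With λ = −ln(1−R)/25, a leaver's chance of a recorded event is L = 1 − R/(25λ). Then P(event recorded) = sR + (1−s)L. For R = 50%: L = 1 − 0.5/0.693 = 0.279; taper 0.40×0.5 + 0.60×0.279 = 36.7%; XR-NTX 0.77×0.5 + 0.23×0.279 = 44.9%.

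| R | L | Taper | XR-NTX | OR (truth 1) |
|---|---|---|---|---|
| 50% | 0.279 | 36.7% | 44.9% | 1.40 |
| 70% | 0.419 | 53.1% | 63.5% | 1.54 |
| 90% | 0.609 | 72.5% | 83.3% | 1.89 |

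The unadjusted yes/no test at 25 per arm rejects about 11%, 13% and 16% of the time instead of 5%.

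**Case 2: as case 1, but only half of failures leave.** The leaving fractions become 0.30 and 0.115. For R = 50%: 0.70×0.5 + 0.30×0.279 = 43.4% vs 0.885×0.5 + 0.115×0.279 = 47.4%, OR 1.18. For R = 90% the OR is 1.50.

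**Case 3: events mainly in the first 5 weeks, all failures leave evenly.** Take a 50% risk in weeks 0 to 5 and none later. One fifth of leavers go in those weeks, with average risk 0.279; the rest have the full 0.5. L = 0.2×0.279 + 0.8×0.5 = 0.456. Taper: 0.40×0.5 + 0.60×0.456 = 47.3%. XR-NTX: 0.77×0.5 + 0.23×0.456 = 49.0%. OR 1.07. Adding a 10% risk over weeks 5 to 25 gives an OR of about 1.1.

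**Case 4: XR-NTX patients leave early.** Constant hazard; 40% of XR-NTX leave at week 1; half of the taper arm leaves evenly between weeks 5 and 25. For R = 30%, 50% and 70% the OR is 0.70, 0.63 and 0.53.

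**Case 5: equal leaving in both arms.** The OR is 1.00.

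**Testing the alternatives.** Under a constant hazard, a person-week rate comparison behaves well: in simulation the rate ratio is 1.00 to 1.01 and false positives are 5.1% to 5.7%. Under case 3 it does not. Person-weeks to first event or exit, ∫S(t)[1 − (1−s)t/25]dt, where S(t) is the chance of no event by week t, come to 9.82 (taper) and 12.15 (XR-NTX) per patient. The rates are 0.473/9.82 = 0.0482 and 0.490/12.15 = 0.0403, a ratio of 0.84 where the truth is 1. That is further from 1 than the yes/no OR of 1.07, because the longer-followed arm is credited with low-risk weeks. A Kaplan-Meier comparison of time to first event does not assume a constant rate and avoids this.

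**The case against.** The strongest reply is that unequal observation is not established. SAP C1 says that all patients are followed for 25 weeks. Patients removed for medical reasons or who ask to withdraw stay in open treatment (Protocol, Criteria for Early Discontinuation; SAP F3). Prize draws continue when medication is stopped for adverse events (Protocol, Compensation), the Locator Form supports follow-up of dropouts, and relapsers are offered buprenorphine and transferred only once stable (SAP F1, F3). A patient can fail the primary outcome and still be fully observed. All of this stands as a reason to treat the problem as conditional. None of it says that SAFTEE is still administered after exit, so the gap remains.

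A reader might go further and infer that the SAP expects failure of 60% vs 23%, so that XR-NTX is bound to look more toxic merely by retaining patients. The documents do not support that. The 40% vs 77% pair is an example of a detectable difference, offered only for sample size; the stated hypothesis is just that more patients succeed on XR-NTX. Early departures during induction would push the odds ratio the other way.

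Two further replies carry weight. Induction takes one week, the taper ends at week 5 and the last injection comes 8 weeks after the first, so events may be front-loaded and the distortion small, as case 3 shows. And this is a secondary outcome in an exploratory trial of about 50: at 25 per arm an OR of 1.40 has a 95% interval of roughly 0.45 to 4.4. The percentage with a recorded event also remains a legitimate description of each arm.

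**Conclusion.** The concern holds in conditional form. The planned comparison ignores time observed, the documents allow exit before week 25, and they do not say that SAFTEE continues afterwards. If observation time differs by arm, the odds ratio is not a clean measure of event risk.

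The size cannot be fixed from the documents. The illustrations run from about 1.1 to 1.9 against XR-NTX, and from 0.5 to 0.7 if XR-NTX patients leave early, where the truth is 1. They rest on assumed event timing and leaving patterns, equal hazards, and failure as a proxy for leaving. If SAFTEE is collected to week 25 in everyone, or leaving is equal in the two arms, there is no distortion. The primary result is unaffected; what changes is how the pilot's safety comparison reads. The change should be made because a sounder analysis is available from data already planned.

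**What to change.** In SAP C3:

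- Take adverse events out of the logistic-regression sentence. Compare them by assigned arm as time from randomisation to first event, using recorded onset dates and censoring at the last SAFTEE assessment. Report Kaplan-Meier incidence at week 25 and a hazard ratio, each with a 95% CI.
- Keep the yes/no percentages as description, beside weeks observed per arm.
- State whether SAFTEE continues after relapse or exit.
- Do not make a constant-rate Poisson comparison per person-week the main alternative, since it is biased when events are front-loaded.
- Tabulate adverse events by reason for exit. Censoring at exit may be informative: the Protocol's Background links withdrawal-like symptoms to giving up the discontinuation attempt. The time-to-event analysis does not cure this.

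The cost is SAP wording and modest analysis work. Onset dates and termination dates are already collected, and no clinical rule changes.

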We plan to enroll 60 participants into the study. Both males and females will be recruited. All eligible subjects are accepted; however, past experience with recruitment for other studies in this population, it is estimated that the sample will be 75% male, 60% Caucasian, 30% Hispanic or Latino, and 10% Black or African-American. These proportions are consistent with the clinical population of heroin or prescription opioid users in the city of New York and participants that we recruited in our recent treatment studies. We will make every effort to recruit minority patients in order to ensure the generalizability of our findings to the overall treatment population.

C. DATA MANAGEMENT AND ANALYSIS

C1. Data Acquisition and Transmission

Potential subjects will undergo a screening visit which will include a demographics questionnaire, medical history, physical examination, psychiatric evaluation, laboratory testing, and electrocardiogram. The MINI International Neuropsychiatric Interview will be conducted to determine current DSM-5 diagnoses. Eligible participants will be offered the opportunity to participate in the research treatment study and informed consent using the IRB-approved consent form will be obtained by the research psychiatrist.

This is an open-label randomized outpatient trial to evaluate feasibility and efficacy of a new strategy that involves rapid discontinuation of the maintenance buprenorphine dose followed by a brief course of treatment with XR-NTX and to compare it to the standard method of gradual buprenorphine taper. All patients will be followed for 25 weeks to evaluate longer-term outcomes. This is an exploratory study to collect evidence that could be used in designing a definitive efficacy trial.

The study will be entirely outpatient. Upon study entry, participants will begin clinic visits at the Substance Treatment and Research Service (STARS) clinic. All participants will visit the clinic twice weekly to provide urine toxicology, report on adverse events, and complete additional assessments (Table 1). All participants will also receive medical management, a medication adherence focused psychosocial intervention that facilitates compliance with study medication and other study procedures, and promotes abstinence from opioids and other substances.

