In this procedure withdrawal is then precipitated through administration of oral naltrexone and treated with clonidine (an alpha--2--adrenergic receptor agonist which reduces sympathetic nervous system output produced by opiate withdrawal), clonazepam (a benzodiazepine which reduces the anxiety and dysphoria and permits sleep) and other adjunctive medications. In the proposed protocol the risk of severe withdrawal has been minimized by starting naltrexone at the very low dose. Opiate withdrawal causes agitation, elevated pulse and blood pressure and other signs of sympathetic arousal, and sometimes confusion. Clonidine may produce somnolence or hypotension. Clonazepam commonly may produce somnolence. The procedure is contraindicated in patients with unstable medical problems or histories of hypersensitivity to any of the medications used, and these are exclusions in the proposed study. The procedure is conducted in the outpatient setting that permits close monitoring of vital signs and mental status for up to 8 hours daily.

Pregnancy

Buprenorphine and naltrexone are Pregnancy category C agents, although the safety of buprenorphine in pregnancy has been supported in clinical trials (Jones et al., 2010). Female participants will be required to use adequate methods of birth control (condom with spermicide, diaphragm with spermicide, birth control pills) to be included in the study and will be strongly encouraged to use more effective methods like a subdermal implant, IUD, or a depot contraceptive injection. Serum pregnancy tests will be evaluated at baseline and urine for pregnancy will be tested as clinically indicated during treatment according to standard clinical procedures. If a female patient does become pregnant she will be withdrawn from study medication and offered continuing treatment with methadone or buprenorphine, which remains the current treatment of choice for pregnant opioid dependent patients.

Randomization to injection naltrexone or buprenorphine taper

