Female participants who are engaging in sexual activity with men must use adequate methods of contraception which will be discussed repeatedly during the screening process. Serum pregnancy tests will be conducted during screening and urine pregnancy tests will be performed monthly during the study. If a female participant does become pregnant or wishes to become pregnant, study medication will be immediately discontinued, she will be withdrawn from the study, and offered continuing non-pharmacological treatment (psychotherapy).

3) Procedures to Minimize Other Risks:

With regards to the risks of blood draws, only staff trained in phlebotomy will draw blood from participants to minimize risks of infection. Participants will be warned of the possible associated discomfort and slight bruising following blood draws. They can decline blood draws at any time.

We aim to reduce the risk of using cash card reimbursements and incentives to buy drugs by keeping reimbursements at a low monetary value. The monetary incentives for completion of study related activities are felt to be modest, appropriate, and limited and also in card form. This payment schedule has been used successfully in treatment studies in our clinic and others with no observed effect of increased drug use.

With regards to risks associated with interviews, rating scales, and questionnaires, patients are informed that they may refuse to answer any questions and may ask to stop at any time. If participants become upset during the interviews/assessments, assistance will be made available to them.

4) Relapse during outpatient naltrexone induction

During the detoxification phase of the study, particularly during washout day and during first few days when naltrexone is introduced if a patient resumes regular opiate, including buprenorphine, use then taking naltrexone, particularly naltrexone injection, may precipitate opiate withdrawal, which may be severe. Patients will be warned not to take the naltrexone if they resumed any level of opiate use, and opiate abstinence will be confirmed by urine toxicology prior to administering the next daily dose of naltrexone.

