Study Discontinuation

Criteria for removal from the study will include:

(1) substantial alcohol and other drug use that endangers the patient or requires a higher level of care such as inpatient or residential treatment; (2) psychiatric or medical deterioration that cannot be managed safely in the context outpatient treatment offered at the study clinics (e.g., acute suicide risk, acute medical problems); (3) Ongoing non-adherence with recommended clinical visits, absence from the clinic for more than 21 days; and (4) Pregnancy.

Patients who are exited from the trial for any reason will be offered a continued treatment in the community unless a higher level of care is indicated (inpatient or residential treatment), or the patient requests treatment elsewhere, in which care help with arranging referrals will be offered. Participants will be offer a weekly supply of buprenorphine for up to 30 days if they are being transitioned to another treatment program if they are removed from the trial. A clinic staff member, with physician backup, is available 24 hours per day by phone in case of emergency.

Participants may be removed from the trial if they repeatedly miss scheduled appointments or clinical worsening necessitates more intensive treatment (drop out criteria are defined above). Subjects who develop serious psychiatric symptomatology (e.g., psychosis, suicidal ideation, severe depressive symptoms) during the study period will be dropped from the study and appropriate clinical referrals will be made. A patient who's continued opioid use, places them at risk for self-destructive behavior or otherwise places them at significant risk will be discontinued from the study. This would include, but not be limited to, patients who become unconscious after using, engage in destructive or violent behavior while intoxicated, report driving while intoxicated, or develop medical complications from their opioid use. In all cases where subjects are discontinued from the study, the clinical research staff will assume clinical responsibility for the subjects until clinical referrals are operational.

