In case that the patient is removed from the research trial for medical reasons, or is requesting withdrawal from the study, he/she will be retained in open treatment for the remaining study period. Upon removal of a patient from the trial due to clinical deterioration, the patient will be referred for appropriate follow-up treatment, in most instances either intensive outpatient or residential treatment. The PI or a study psychiatrist is available 24 hours/day by phone and/or beeper in case of emergency.

If a patient is discontinued from the study, or decides to withdraw, or relapses during study the participation, the patient will get treated with buprenorphine until they are linked with a referral for continuing buprenorphine treatment. Participants will receive a one-week supply of buprenorphine at a time during the transition process.

Management of SAE's

Serious adverse events (SAEs), as defined by the FDA, will be systematically evaluated at each clinic visit. Any SAE, whether or not related to study medication, will be reported to the IRB and NIDA. The initial SAE report will be followed by submission of a completed SAE report to both institutions.

In the event that a patient either withdraws from the study or the investigator decides to discontinue a patient due to SAE, the patient will have appropriate follow-up medical monitoring. Monitoring will continue until the problem requiring hospitalization has resolved or stabilized with no further change expected, is clearly unrelated to study medication, or results in death. Outcome of SAEs will be reported to NIDA as soon as this information becomes available. A summary of the SAEs that occurred during the previous year will be included in the annual progress report to NIDA.

G. TRIAL EFFICACY

Interim analyses are not planned for this study.

H. DATA AND SAFETY MONITORING PLAN ADMINISTRATION

H1. Responsibility for data and safety monitoring

The study Principal Investigator, [name], is primarily responsible for the data and safety monitoring. He will be assisted by [name], study Medical Monitor, and other STARS staff physicians.

H2. Frequency of DSM

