Ongoing data and safety monitoring will be conducted weekly during research meetings. Every three months, the PI and the medical monitor will review the number of patients enrolled, the number who completed the protocol, the number who dropped out of the protocol prior to completion (and reason why), any adverse events, procedures for assuring patient privacy and confidentiality, and the quality and integrity of the data collected. Corrective action will be taken if needed. IRB protocols and informed consent documents will be reviewed annually by the IRB. Reports of enrollment and retention and reporting of adverse events are required with these renewals. In addition, all studies involving human subjects are periodically and systematically reviewed by the New York State Quality Assurance Staff. These procedures assure protocol compliance by conducting unannounced reviews of participants' research charts, comparing research charts to the IRB protocol. All serious adverse events will be reported to the DSMB in a timely fashion. This report will also be forwarded to the NIDA's Project Staff [name] (PO) upon receipt.

In addition, a separate Data Safety and Monitoring Board (DSMB; see below for details) will meet yearly.

H3. Content of DSM report

Annually, the DSMB will prepare and submit a report to NIDA. This report will include the following:

1. Brief description of the trial
2. Baseline socio-demographic characteristics
3. Retention and disposition of study participants
4. Q.A. Issues
5. Regulatory Issues
6. AEs
7. SAEs
8. Efficacy

I. DSM BOARD PLAN

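### SAP F3 offers a pregnant participant only psychotherapy, while SAP F1 and the Protocol offer methadone or buprenorphine

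*SAP*

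**What the plan says.** Two SAP passages and one Protocol passage say what a participant is offered if she becomes pregnant.

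- **SAP F3, Procedures for Minimizing Risks, item 2 (Study Procedures).** The trigger is "If a female participant does become pregnant or wishes to become pregnant". The consequence is that "study medication will be immediately discontinued, she will be withdrawn from the study, and offered continuing non-pharmacological treatment (psychotherapy".
- **SAP F1, Pregnancy.** On becoming pregnant, a participant comes off study medication. She is then to be "offered continuing treatment with methadone or buprenorphine, which remains the current treatment of choice for pregnant opioid dependent patients".
- **Protocol, Risks/Discomforts/Inconveniences, Pregnancy.** The same rule as SAP F1, in the same words.

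Pregnancy is also a criterion for removal: in the Protocol under Criteria for Early Discontinuation and again under its procedures for minimizing risks, and in the SAP under Study Discontinuation. For a participant who is discontinued, withdraws or relapses, the SAP (Study Discontinuation) and the Protocol (Criteria for Early Discontinuation) both say that "the patient will get treated with buprenorphine until they are linked with a referral for continuing buprenorphine treatment".

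**The concern.** For one event, the SAP names two different follow-on treatments. The passage that names only psychotherapy sits under risk-minimizing procedures, where clinic staff would naturally look for what to do. The passage that names an agonist sits in the description of risks. A staff member who went no further than F3 would stop buprenorphine at once and offer therapy alone, which is not the care that the plan itself calls the treatment of choice in pregnancy.

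What is at stake is participant safety. SAP F1, in the paragraphs on buprenorphine risks, links stopping buprenorphine to relapse and to overdose risk. That bears most directly on a woman who is taking study buprenorphine when the pregnancy is detected.

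**Working it through.** The point is textual, and the plan gives no figure to reproduce. The passages side by side:

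| Place | Trigger | Status | Treatment named |
|---|---|---|---|
| SAP F3, item 2 | Pregnant, or wishes to be | Medication stopped, out of the study | Psychotherapy only |
| SAP F1, Pregnancy | Pregnant | Off study medication | Methadone or buprenorphine |
| Protocol, Pregnancy | Pregnant | Off study medication | Methadone or buprenorphine |
| SAP F3, Study Discontinuation | Any discontinuation, withdrawal or relapse | Discontinued or relapsed | Buprenorphine until linked |
| Protocol, Criteria for Early Discontinuation | Same | Same | Buprenorphine until linked |

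1. **Is it a real conflict?** Yes. All five rows are current text. Four name an agonist, and only SAP F3 item 2 does not.
2. **Which passage should give way?** SAP F3 item 2. It disagrees with the SAP's own Pregnancy paragraph and with the Protocol. SAP H2 describes chart audits made by "comparing research charts to the IRB protocol", so the Protocol is the standard that care will be checked against.
3. **Does the general rule reach a pregnant participant?** Yes. Pregnancy is a listed removal criterion in both documents, so she is discontinued and the last two rows apply to her.
4. **What about someone who only wishes to become pregnant?** SAP F1 and the Protocol's Pregnancy paragraph do not mention her. If she is withdrawn, the general rule in the last two rows covers her.
5. **When would the conflict matter most?** While she is taking study buprenorphine. The planned schedule is 4 weeks of stabilization plus 25 weeks after randomization, so 4 + 25 = 29 weeks.
   - Taper arm: 4 + 5 = 9 weeks on buprenorphine, 9/29 = 31%.
   - XR-NTX arm: about 4 weeks, 4/29 = 14%.

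   These are shares of planned time. They are not probabilities of pregnancy.

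**The case against.** The strongest reply is that nothing is withheld. SAP F3 item 2 does not prohibit an agonist, and its offer of continuing psychotherapy can be read as carrying on the therapy she already receives, alongside agonist care. Staff are equally bound by the Pregnancy paragraph and the discontinuation rule. Both documents also keep clinical responsibility with the research staff until referrals are working. The audit against the Protocol is a further safeguard. All of this stands, and it is why the harm is limited. It does not remove the contradiction: a sentence that stops study medication at once and names only non-drug care points away from the other passages.

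A reader might infer three stronger things that the documents do not support.

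- **That pregnant participants would be denied agonist treatment.** This follows only if item 2 is applied alone and the other passages are ignored.
- **That methadone or buprenorphine should be offered to a woman who only wishes to conceive.** The treatment-of-choice statement concerns pregnant patients, and no passage extends it to her.
- **That the SAP's other supply provision is a second defect.** Study Discontinuation offers removed participants "a weekly supply of buprenorphine for up to 30 days if they are being transitioned to another treatment program". This differs from the until-linked rule only for someone still unlinked after day 30. The documents give no time to linkage, and the clinical-responsibility clause covers that person too.

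**Conclusion.** The inconsistency is certain and its consequence is small. SAP F3 item 2 conflicts with the SAP's own Pregnancy paragraph, with the Protocol's, and with the discontinuation rule in both documents. Inferior care would follow only if staff used item 2 alone, and mainly for a woman then taking study buprenorphine.

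The number of participants affected cannot be estimated, because neither document gives a pregnancy rate. Counting the women expected in the sample would not measure it.

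The conclusion assumes that both documents were in force together and that staff may consult the SAP's risk-minimizing section on its own. It is a wording correction in a safety section. Endpoint, sample size and analysis are unaffected.

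**What to change.** Amend the sentence in SAP F3, item 2. Keep withdrawal from the study, because pregnancy is a removal criterion in both documents, and add the agonist offer. For example:

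> *If a participant becomes pregnant, study medication will be discontinued, she will be withdrawn from the study and offered continuing treatment with methadone or buprenorphine (see Pregnancy, F1) together with psychotherapy. A participant taking buprenorphine will be supplied with it until she is linked to that treatment.*

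For a participant who only wishes to become pregnant, refer to the existing discontinuation rule and add no new offer.

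The cost is this one SAP edit. The supply rule it invokes is already a commitment in both documents, so it adds no visits, drug supply or statistical work. The 30-day provision in the SAP and the Protocol text can stay as they are.
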